2.3.2. Secondary Endpoint(s)

Safety endpoints include ECG assessments (QT, PR, QRS, RR, and QTc [QTcB, QTcF] intervals), vital sign measurements, clinical laboratory tests, adverse events, and findings from physical examinations

2.3.3. Exploratory Endpoint

[figure not shown]
Not applicable

3. STUDY DESIGN

3.1. Overall Design

3.1.1. Overview

Figure 3.1: Schematic Chart of Study Design

3.1.2. Dose Escalation Process

Not applicable.

3.1.3. Study Stopping Criteria

Not applicable

3.2. Discussion of Study Design

4. STUDY POPULATION

4.1. Inclusion Criteria

Subjects must satisfy all of the following criteria to be included in the study:

1. Healthy male and female subjects between 18 and 60 years (y) of age, inclusive.
2. BMI of 18 to 30 kg/m², inclusive.
3. Good health as determined at Screening and Check-in by examining medical history (Screening only) and performing physical examinations, vital signs, ECGs, serum chemistry, hematology, coagulation tests (Screening only), virology (Screening only), and urinalysis.
4. Negative serum pregnancy test at Screening and during Check-in for female subjects.
5. Female subjects must be:
 - Surgically sterile (documented hysterectomy, bilateral tubal ligation, or bilateral salpingo-oophorectomy, Essure® with hysterosalpingogram [documentation to confirm tubal occlusion 12 wk after procedure])

OR

- Naturally postmenopausal (spontaneous cessation of menses) for at least 12 consecutive mo prior to dosing, with a follicle stimulating hormone (FSH) level at Screening of ≥40 mIU/mL

AND

- Nonlactating

6. Male subjects must be:

- Surgically sterile (confirmed by documented azoospermia 90 d after the procedure)

OR

- Agree to use double barrier methods of contraception from Check-in until 90 d after the final dose of pexidartinib. Adequate methods of contraception for subjects or partners include: condom with spermicidal gel, diaphragm with spermicidal gel, and abstinence. If a subject is not sexually active but becomes active, he and his partner must use the above listed double barrier methods of contraception. Male subjects must not donate sperm during the study and for up to 90 d after the final dose.

7. Negative urine test for drugs of abuse (opiates, benzodiazepines, amphetamines, cannabinoids, cocaine, barbiturates, and phencyclidine), cotinine, and alcohol at Screening and Check-in.
8. Negative test result for human immunodeficiency virus (HIV) antibody, hepatitis B surface antigen (HBsAg), and hepatitis C virus (HCV) antibody at Screening.

9. Willingness to refrain from consuming food or beverages containing caffeine/xanthine or alcohol for 48 h prior to Check-in on Day -1 until the end of the study.
10. Willingness to refrain from consuming grapefruit/grapefruit juice and Seville oranges 7 d before the first dose of study drug on Day 1 until the end of the study.

4.2. Exclusion Criteria

Subjects who meet any of the following criteria will be disqualified from entering the study:

1. History of any clinically significant disorder, including cardiovascular, hematologic, pulmonary, hepatic, renal, gastrointestinal, connective tissue disease, uncontrolled endocrine/metabolic, oncologic (within the last 5 y), neurologic, and psychiatric diseases, or any disorder that may prevent the successful completion of the study.
2. History of stomach or intestinal surgery or resection that would potentially alter absorption and/or excretion of orally administered drugs (with the exception of appendectomy, hernia repair, and/or cholecystectomy).
3. History of clinically significant neutropenia.
4. Use of any prescription medications/products and any medications known to induce or inhibit CYP and UGT enzymes within 28 d from the first dose and during the study (see Section 16.5 for a list of drug products that inhibit/induce CYP and UGT enzymes).
5. Use of food or beverages containing grapefruit 7 d prior to dosing and during the study.
6. Use of over the counter (OTC), nonprescription medication (including vitamin D preparations and calcium) within 14 d from the first dose and during the study (excluding acetaminophen (≤ 2 g/d)).
7. Use of supplements (including phytotherapeutic/herbal/plant-derived preparations and most vitamins and minerals) within 14 d from the first dose and during the study.
8. Use of or caffeine-containing foods or beverages within 48 h prior to Check-in and during confinement.
9. Consumption of alcohol within 48 h prior to Check-in and during confinement.
10. Laboratory results (serum chemistry, hematology, and urinalysis) outside the normal range, if considered clinically significant by the investigator. Liver function test results (ALT, AST, total bilirubin) greater than the upper limit of normal. Hemoglobin levels must be ≥ 11.5 g/dL for female subjects and ≥ 12.5 g/dL for male subjects.
11. Estimated glomerular filtration rate (eGFR) (using the Cockcroft-Gault equation) < 90 mL/min at Screening.
12. History or presence of an abnormal ECG, which, in the investigator's opinion, is clinically significant and/or a corrected QT interval using Fridericia's formula (QTcF) ≥ 450 msec for males and ≥ 470 msec for females at Screening.
13. Blood donation of 500 mL or more or a significant loss of blood within 56 days prior to the first dose.
14. Receipt of a transfusion or any blood products within 30 days prior to the first dose.

15. Current participation in another investigational study or who have participated in an investigational study within the past 30 days prior to the first dose.
16. Consumption of more than 28 units of alcohol per wk (males) or 14 units of alcohol per wk (females), where 1 unit of alcohol equals 1/2 pint of beer, 4 ounces of wine, or 1 ounce of spirits, or significant history of alcoholism or drug/chemical abuse within the last 2 y.
17. Use of tobacco products or nicotine-containing products (including smoking cessation aids, such as gums or patches) within 6 mo prior to the first dose.
18. Positive results on tests for drugs of abuse, cotinine or alcohol at Screening or Check-in.
19. Positive test result for HBsAg, HCV antibody, or HIV antibody.
20. Employment by the clinic.
21. Unable to consume or allergic to the breakfast meal
22. Any other reason, in the opinion of the investigator, that precludes subject participation in the study.
23. Familial relationship with another study participant.

Subjects must be compliant with all inclusion and none of the exclusion criteria

5. STUDY TREATMENT(S)

5.1. Assigning Subjects to Treatment Group(s) /Sequences and Blinding

5.1.1. Treatment Group(s) /Sequences

Subjects will be randomized to 1 of 6 sequences: ABC, ACB, BAC, BCA, CAB, and CBA.

The study treatments include:

- Treatment A: Single oral 400 mg (2 × 200 mg capsules) of pexidartinib in the morning with 240 mL of water after an overnight fast of 10 h
- Treatment B: Single oral 400 mg (2 × 200 mg capsules) of pexidartinib in the morning within 30 min of a low-fat standard breakfast meal
- Treatment C: Single oral 200 mg (1 × 200 mg capsule) of pexidartinib in the morning within 30 min of a low-fat standard breakfast meal

5.1.2. Method of Treatment Group(s) /Sequences Allocation

This is an open-label randomized study. The randomization schedule will be produced by a statistician from Worldwide Clinical Trials, under the specification approved by the sponsor statistician. A dummy schedule will first be produced and will be checked by the sponsor statistician. Prior to the start of the study, a copy of the randomization schedule will be supplied by the Worldwide Clinical Trials statistician to the clinical site pharmacist and at an appropriate time to the bioanalytical division at Celerion.

5.1.3. Blinding

Not applicable. This is an open-label study.

5.1.4. Emergency Unblinding Procedure

Not applicable.

5.2. Study Drug

5.2.1. Description

Pexidartinib 200 mg capsules will be provided by the sponsor in open-labeled bottles.

5.2.2. Labeling and Packaging

Pexidartinib 200 mg bottles will be labeled in compliance with regulatory requirements. The packaging will clearly display the name of the study drug, the lot number, storage condition, and other required information in accordance with local regulations.

5.2.3. Preparation

The study drug will be supplied as capsules that need no further preparation at the study site.

5.2.4. Administration

Pexidartinib will be administered orally in the clinic with approximately 240 mL of water.

The study product will be administered in accordance with the protocol. Study product will be administered only to subjects participating in the clinical study. It is a violation of the regulations to use unapproved study product for purposes other than the protocol.

The site will complete the required documentation as provided by Daiichi Sankyo, Inc. (DSI) or its representatives to document dispensing of the study products. All information will be recorded immediately on a drug dispensing form each time the study products are dispensed to a subject

5.2.5. Storage

Drug supplies must be stored in a secure, limited access storage area under the recommended storage conditions.

Pexidartinib 200 mg capsules should be stored at 20°C to 25°C (68 °F to 77°F). Excursions are permitted to 15°C to 30°C (59°F to 86°F). Capsules should not be frozen.

5.2.6. Drug Accountability

When a drug shipment is received, the investigator or designee will check the amount and condition of the study drug, check for appropriate local language in the label and supporting documentation, and sign the Receipt of Shipment Form provided. The Receipt of Shipment Form should be faxed as instructed on the form. The original will be retained at the site.

In addition, the investigator or designee shall contact DSI as soon as possible if there is a problem with the shipment.

A Drug Accountability Record will be provided for the pexidartinib study product. The record must be kept current and should contain the dates and quantities of drug received, each subject's identification number and/or initials or supply number as applicable, to whom the investigational medicinal product were dispensed, the date and quantity of investigational medicinal product dispensed and remaining, if from individual subject drug units as well as the initials of the dispenser.

At the end of the study, or as directed, the investigator will arrange for the destruction of unused, partially used, or empty containers of pexidartinib study product. During the site approval process, appropriate and acceptable destruction procedures will be verified. If absolutely necessary and after DSI approval, drug (used/unused) may be returned to DSI or a designee as instructed by DSI.

If in the event the investigational medicinal products are returned for some pre-approved reason, the investigational medicinal product will be returned only after the study monitor has completed a final inventory to verify the quantity to be returned. The return of investigational medicinal product must be documented, and the documentation included in the shipment. At the end of the study, a final investigational medicinal product reconciliation statement must be completed by the investigator or designee and provided to the sponsor.

All investigational medicinal product inventory forms must be made available for inspection by a sponsor authorized representative or designee and regulatory agency inspectors. The investigator is responsible for the accountability of all used and unused study supplies at the site.

5.2.7. Retention Samples

Not applicable.

5.3. Control Treatment

Not applicable.

5.4. Dose Interruptions and Reductions

Not applicable

5.5. Method of Assessing Treatment Compliance

In order to ensure treatment compliance, all doses will be administered under the supervision of clinical study personnel. A mouth and hand check of all subjects should be carried out to ensure that all capsules have been swallowed.

5.6. Prior and Concomitant Medications

Medications used 30 d prior to Screening will be recorded.

The following medications and products will be prohibited:

- Any prescription medications/products and any medications known to induce or inhibit CYP and UGT enzymes within 28 d from the first dose and during the study (see Section 16.5 for a list of drug products that inhibit/induce CYP and UGT enzymes).
- Any OTC, nonprescription medications (including vitamin D preparations and calcium) within 14 d from the first dose and during the study. However, topical hydrocortisone will be allowed for contact dermatitis, and prune juice will be allowed for constipation.
- Use of supplements (including phytotherapeutic/herbal/plant-derived preparations and most vitamins and minerals) within 14 d from the first dose and during the study.

Acetaminophen (≤ 2 g/d) is allowed during confinement at the discretion of the investigator.

Any medication (other than study drugs) taken by subjects during the course of the study will be recorded and coded using the World Health Organization (WHO) dictionary. If drug therapy other than that specified by the protocol is taken, a joint decision will be made by the investigator and sponsor whether to continue or discontinue the subject.

5.6.1. Dietary and Lifestyle Restrictions

At Screening, subjects will be informed that if accepted for the study, no foods or beverages containing grapefruit is allowed for 7 d prior to dosing and throughout the study, and alcohol is

prohibited for 48 h prior to Check-in and during confinement. Subjects must also agree to abstain from caffeine-containing foods or beverages from 48 h prior to Check-in and during confinement.

Treatment A:

Subjects will be required to fast overnight for at least 10 h prior to dosing.

Treatment B and Treatment C:

Subjects will be required to fast overnight for at least 10 h until 30 min prior to dosing, when they will be given a standard low-fat breakfast which will be entirely consumed within 30 min. The breakfast will consist of 8 ounces of 1 percent fat milk, 1 boiled egg, and one packet of instant flavored oatmeal made with water.

Subjects should be dosed within 5 minutes of completing the meal.

For all treatments:

Following dosing, subjects will be required to fast for at least 4 h. A standard menu and meal schedule (based on United States Recommended Daily Allowance) will be administered uniformly to all subjects. Meals and/or snacks will be served at appropriate times following dosing. Identical meals will be served for each treatment (except for the test breakfast). The calorie content, as well as the percent of calories from protein, carbohydrate, and fat, will be uniform for each meal during the study (ie, breakfast uniform to breakfast, lunch uniform to lunch).

Water will not be permitted from 1 h before until 2 h after dosing (with the exception of 240 mL of water administered with dosing and the liquid given with breakfast), but will be allowed at all other times.

Except when ECGs must be taken in supine position, subjects will remain seated in an upright position with minimal ambulation (ie, only to and from the washroom or for study procedures) for the first 4 h following dosing. When ECGs assessment and PK samples are scheduled at the same time, ECG will be done first followed by PK sampling.

5.7. Subject Withdrawal/Discontinuation

5.7.1. Reasons for Withdrawal

Any subject who discontinues from the study treatment for any reason will have their study treatment discontinuation recorded.

Following randomization, subjects may be withdrawn before completing the study per protocol for any of the following reasons:

- AE
- Withdrawal of consent by subject
- Physician decision
- Pregnancy

- Protocol deviation
- Study terminated by sponsor
- Other

All subjects who are withdrawn from the study should complete protocol specified withdrawal procedures (Section 6.6).

5.7.2. Withdrawal Procedures

In accordance with the Declaration of Helsinki and other applicable regulations, a subject has the right to withdraw from the study at any time and for any reason without prejudice to his or her future medical care by the study physician or at the study site.

If a subject withdraws from the study, s/he will be required to have Early Termination study procedures performed (refer to Section 6.6).

If a subject is withdrawn from the study, the investigator will complete and report the observations as thoroughly as possible up to the date of withdrawal, including the date of last treatment and the reason for withdrawal.

If the subject is withdrawn due to an AE, the investigator will follow the subject until the AE has resolved or stabilized.

All subjects who are withdrawn from the study should complete protocol-specified withdrawal procedures.

5.7.3. Subject Replacement

There is no plan for subject replacement.

5.7.1. Subject Re-screening Procedures

Not applicable.

5.8. Criteria for Suspending Study Treatment

Not applicable.

6. STUDY PROCEDURES

6.1. Screening

Screening will be conducted anytime within 21 d prior to dosing. Informed consents (general study procedures/genotyping and the Health Insurance Portability and Accountability Act [HIPAA]⁴) will be obtained from the subject prior to performing any of the Screening assessments.

The following activities and/or assessments will be performed at Screening:

- Informed consent
- Inclusion/exclusion criteria
- Medical history
- Prior and concomitant medication history
- Complete physical exam
- Height and body weight (and BMI calculation)
- 12-lead ECG
- Vital signs (blood pressure, heart rate, oral temperature, and respiratory rate)
- Blood samples for:
 - HIV antibody
 - HBsAg and HCV antibodies
 - Clinical laboratory tests (hematology and fasting serum chemistry); subjects will fast for approximately 10 h prior to Screening for the serum chemistry tests
 - Coagulation tests (prothrombin time [PT] / INR and activated partial thromboplastin time [aPTT])
 - Serum pregnancy test for all females
 - FSH test for naturally postmenopausal female subjects
- Urine samples for:
 - Urine drug screen (opiates, benzodiazepines, amphetamines, cannabinoids, cocaine, barbiturates, phencyclidine), cotinine, and alcohol
 - Clinical laboratory tests (urinalysis)
- Calculation of eGFR (using the Cockcroft-Gault equation)

6.2. Subject Management

Not applicable.

6.4. Treatment Period

6.4.1. Day -1 of Period 1 Check-in

A sufficient number of alternate subjects will be brought into the clinic at Check-in (Day -1) of Period 1. Alternate subjects will undergo all baseline assessments. In the event that a subject scheduled to be randomized cannot be dosed, an alternate subject will be assigned the same randomization number and sequence of treatments.

The following procedures will be carried out at Check-in:

- Admission to clinic
- Inclusion/exclusion criteria
- Abbreviated medical history (applicable to Period 1 only, since Screening) and concomitant medication history
- Complete physical exam
- Body weight
- Blood samples for:
 - Clinical laboratory tests (hematology and fasting serum chemistry); subjects will fast for approximately 10 h prior to Check-in for the serum chemistry tests
 - Serum pregnancy test for all females
- Urine samples for:
 - Drug screen (opiates, benzodiazepines, amphetamines, cannabinoids, cocaine, barbiturates, phencyclidine), cotinine, and alcohol
 - Clinical laboratory urinalysis tests

6.4.2. Day 1

The following procedures will be performed on Day 1 of each period:

- Administration of pexidartinib according to the randomization scheme at Time 0; for Treatment A, subjects will fast for approximately 10 h prior to dosing; for Treatment B and Treatment C, subjects will fast for approximately 10 h then consume a standard low-fat meal starting 30 min before dosing.

- Vital signs (blood pressure, heart rate, oral temperature, and respiratory rate) prior to dosing and at approximately 2 h postdose
- 12-lead ECGs prior to dosing and at approximately 2 h postdose
- Blood samples for:
 - PK analysis prior to dosing and at 0.5, 1, 1.5, 2, 2.5, 3, 3.5, 4, 4.5, 5, 6, 8, 10, 12, 14, and 22 h postdose
- Continuous monitoring of AEs, starting from dosing, and concurrent medication

6.4.3. Day 2

The following procedures will be performed on Day 2 of each period:

- Vital signs (blood pressure, heart rate, oral temperature, and respiratory rate) at approximately 24 h postdose
- 12-lead ECGs at approximately 24 h postdose
- Blood samples for PK analysis at 24, 28, 32, and 36 h postdose
- Continuous monitoring of AEs and concurrent medication

6.4.4. Day 3

The following procedures will be performed on Day 3 of each period:

- Blood samples for PK analysis at 48, 54, and 60 h postdose
- Continuous monitoring of AEs and concurrent medication

6.4.5. Day 4

The following procedures will be performed on Day 4 of each period:

- Blood samples for PK analysis at 72 and 84 h postdose
- Continuous monitoring of AEs and concurrent medication

6.4.6. Day 5

The following procedures will be performed on Day 5 of each period:

- Blood samples for PK analysis at 96 and 108 h postdose
- Continuous monitoring of AEs and concurrent medication

6.4.7. Day 6

The following procedures will be performed on Day 6 of each period:

- Blood samples for PK analysis at 120 and 132 h postdose
- Continuous monitoring of AEs and concurrent medication

6.4.8. Day 7

The following procedures will be performed on Day 7 of each period:

- Vital signs (blood pressure, heart rate, oral temperature and respiratory rate) at approximately 144 h postdose
- 12-lead ECGs at approximately 144 h postdose
- Blood sample for PK analysis at 144 h postdose
- Continuous monitoring of AEs and concurrent medication

6.5. Washout

There will be a washout of at least 6 d between each dose of pexidartinib.

6.6. Check-out or Early Termination

The following procedures will be performed at check-out of Period 3 (Day 7) or upon Early Termination:

- Complete physical exam
- Body weight
- Vital signs (blood pressure, heart rate, oral temperature, and respiratory rate), if not already taken
- 12-lead ECGs, if not already taken
- Blood samples for:
 - Clinical laboratory tests (hematology and fasting serum chemistry); subjects will fast for approximately 10 h prior to check-out for the serum chemistry tests
 - Serum pregnancy test for all females
- Urine samples for clinical laboratory urinalysis tests
- Continuous monitoring of AEs and concurrent medication

6.7. Follow-up

If a subject is withdrawn from the study due to an AE, the subject will be asked to complete, at a minimum, assessments of the early withdrawal visit. If the AE has still not resolved, additional follow-up will be conducted, as appropriate, based on the investigator's judgment, and documented in the subject's medical records. At a minimum, serious adverse events (SAEs) should be followed for 30 d after the subject's last dose of study drug.

7. PHARMACOKINETIC ASSESSMENTS

7.1. Pharmacokinetic Assessment(s)

Pharmacokinetic analysis will be conducted in compliance with DSI's noncompartmental analysis guidelines.

The plasma concentration-time data will be analyzed using actual dosing and sampling time points using noncompartmental methods. The PK parameters listed in Table 7.1 will be calculated for pexidartinib from the individual plasma concentrations using a noncompartmental approach. Pharmacokinetic variables will be computed using WinNonlin Professional or other appropriate software.

Table 7.1: Plasma Pharmacokinetic Variables

Parameter	Units	Description
Cmax	ng/mL	Maximum observed plasma drug concentration
Tmax	h	Time of maximum observed concentration
AUClast	ng·h/mL	Area under the plasma concentration-time curve, from time 0 to the last measurable concentration (Clast), as calculated by the log-linear trapezoidal method
AUCinf	ng·h/mL	AUC from the time of dosing extrapolated to infinity, calculated as: $AUC_{inf} = AUC_{last} + Clast/\lambda_Z$, where λ_Z is the apparent terminal elimination rate constant calculated by linear regression of the terminal linear portion of the log concentration versus time curve
AUCextr%	%	Percentage of AUCinf that is extrapolated from tlast to infinity, calculated as: $100 \times [1 - (AUC_{last}/AUC_{inf})]$, where tlast is the time of the last measurable plasma drug concentration
t1/2	h	Terminal elimination half-life, calculated as: $\ln(2)/\lambda_Z$
CL/F	L/h	Apparent total body clearance, calculated as: Dose/AUC
Vz/F	L	Apparent volume of distribution, calculated as: $Dose/AUC_{inf} \times \lambda_Z$

A more detailed description of the pharmacokinetic assessments will be provided separately in the SAP.

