1.2.1.4. Clinical Experience

A comprehensive series of nonclinical and clinical (N=14) studies and analyses elucidated the PK and PD and the influence of intrinsic and extrinsic factors on the PK of pexidartinib human exposure has been evaluated in 6 clinical studies.

Pexidartinib is an orally bioavailable drug with a terminal elimination half-life of 27 hours (h). Pexidartinib is metabolized mainly by UDP-glucuronosyltransferase (UGT)1A4 and cytochrome P450 (CYP)3A and undergoes minimal urinary elimination as unchanged drug. Strong inhibitors of these metabolic pathways increase pexidartinib exposures. CYP3A inducers, like rifampin decreases pexidartinib exposure. Concurrent administration of systemic pH modifiers (eg, esomeprazole) reduces pexidartinib exposure by approximately 40 to 50%. No dose adjustment

is needed for subjects with renal impairment including patients on routine hemodialysis. Administration of pexidartinib with food (high fat meal) increased exposure approximately 2-fold. Therefore, it is recommended to dose pexidartinib twice daily at least 1 h before or 2 h after a meal. Pexidartinib does not prolong the QTc interval.

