1.4. Risks and Benefits for Study Subjects

There is no direct benefit for study subjects in the current study. Indirect benefits to the healthy subjects enrolled in this study are the free medical tests received during Screening and the safety monitoring as mandated by the study.

The PK, safety, and tolerability of single doses of pexidartinib (200 mg to 2400 mg) in approximately 190 healthy subjects have been evaluated in 9 studies. In general, pexidartinib was well-tolerated up to average peak exposure of 20,800 ng/mL and a total exposure (AUC) of 491,948 ng•h/mL (1800 mg fed state) ng•h/mL. No safety signals in vital signs, physical examinations, or ECG recordings, including QT prolongation, were reported.¹ Therefore, the risk for uncovering a new untoward effect of a single dose of pexidartinib is relatively small.

Based on pooled data from the oncology studies with multiple dosing, the most frequent AEs (occurring in >10% of subjects) potentially related to the study drug were fatigue, nausea, decreased appetite, hair color changes, diarrhea, increases in AST and ALT levels, vomiting, anemia, dysgeusia, and rash. At dosage levels \geq 600 mg/d, transient increases in AST and/or ALT levels have been commonly observed with multiple dosing. Among common TEAEs, fatigue, increased AST and ALT levels, anemia, and rash were rated Grade 3 or higher with a frequency greater than 1%¹.

Elevations of liver transaminases and bilirubin have been observed in studies with pexidartinib, together with cases of drug induced cholestatic liver injury following multiple doses. Cases of cholestasis have been observed in the first 8 weeks, have generally resolved with treatment discontinuation, but in rare cases have been severe, requiring liver dialysis and had a protracted course (8 mo).

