2.3. Study Endpoints

2.3.1. Primary Endpoint

Plasma concentration time data for pexidartinib will be analyzed using noncompartmental methods. The following PK parameters will be reported: maximum observed concentration in plasma (Cmax), time to maximum observed concentration (Tmax), and area under the concentration-time curve from time of dosing to last measurable concentration (AUClast) and area under the concentration-time curve from time of dosing to infinity (AUCinf). Terminal half-life (t_{1/2}), apparent total body clearance (CL/F), and apparent volume of distribution (Vz/F) will also be reported.

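### Does the Vz/F formula in Table 7.1 of the protocol give a wrong volume of distribution?

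*Combined protocol and SAP*

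**What the plan says.** Section 2.3.1 of the protocol (Primary Endpoint) lists Cmax, Tmax, AUClast and AUCinf, and adds that half-life, clearance and "apparent volume of distribution (Vz/F) will also be reported".

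Table 7.1 in Section 7.1 gives the definitions:

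- **CL/F**, unit L/h: "Apparent total body clearance, calculated as: Dose/AUC", without saying which AUC.
- **Vz/F**, unit L: "Apparent volume of distribution, calculated as", followed by Dose/AUCinf × λz with no brackets.
- **λz**, in the AUCinf row: it "is the apparent terminal elimination rate constant calculated by linear regression of the terminal linear portion of the log concentration versus time curve".
- **t1/2**, unit h: "Terminal elimination half-life, calculated as" ln(2)/λz.

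Section 7.1 also places the analysis under the sponsor's noncompartmental guidelines and states: "Pharmacokinetic variables will be computed using WinNonlin Professional or other appropriate software". It leaves further detail to the SAP. Section 1.2.1.4 gives a terminal half-life of 27 h.

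**The concern.** By the usual order of operations, Dose/AUCinf × λz means (Dose/AUCinf) × λz. That is clearance multiplied by the rate constant, whereas a volume needs clearance divided by it. The result would carry the wrong unit and a very different number.

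The CL/F row adds a second loose end. The table derives both AUClast and AUCinf, so a clearance taken from AUClast would not satisfy Vz/F = (CL/F)/λz.

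Both parameters appear under the primary endpoint heading and will be summarised for all three treatments. If someone programmed or checked Vz/F literally from the table, a wrong volume could reach the report.

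**Working it through.** The protocol states no value of Vz/F, so there is no figure to reproduce. The check concerns units, then size.

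**Inputs.** Half-life 27 h (Section 1.2.1.4). Units and formulas from Table 7.1. For illustration only, the exposure in Section 1.4: 1800 mg, fed, AUC 491,948 ng·h/mL. Last sample at 144 h (synopsis and Section 6.4.8).

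**1. Units of the two readings.** Dose/AUCinf is in L/h and λz is in 1/h.

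- Left to right: (L/h) × (1/h) = L/h².
- Both terms after the slash in the denominator: (L/h) ÷ (1/h) = L.

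Only the second agrees with the unit printed in the table.

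**2. Size of the difference.** λz = ln(2)/27 = 0.02567 per h. The ratio of the second reading to the first is 1/λz² = (27/0.6931)² = 1517. For other assumed half-lives:

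| Half-life (h) | 1/λz² (h²) |
|---|---|
| 20 | 833 |
| 24 | 1199 |
| 27 | 1517 |
| 30 | 1873 |
| 35 | 2550 |

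This ratio is not a true fold error, because the two readings have different units and it changes with the time unit. In days, λz = 24 × 0.02567 = 0.616 per day and the ratio is 1/0.616² ≈ 2.6.

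**3. What a literal calculation would look like.** Dose/AUC = 1,800,000,000 ng ÷ 491,948 ng·h/mL = 3659 mL/h = 3.66 L/h.

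- Divided by λz: 3.66/0.02567 = 142.5 L.
- Multiplied by λz: 3.66 × 0.02567 = 0.094 L/h².

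A volume of distribution of 0.094, in a column headed L and beside a clearance of 3.66 L/h and a half-life of 27 h, would be noticed at the first check.

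**4. Which AUC for clearance.** With a mono-exponential decline that stays measurable to 144 h, the share of AUCinf beyond the last sample is about exp(−0.02567 × 144) = 0.025. CL/F from AUClast would then be higher by 1/(1 − 0.025) − 1, or about 2.5%. At assumed half-lives of 20 h and 40 h the extrapolated shares are about 0.7% and 8%. Table 7.1 also derives AUCextr%, so the gap between the two areas will be known for each profile.

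**5. Where the parameters are used.** The mixed-model ANOVA and the 90% confidence intervals in Section 10.4.1 cover log Cmax, log AUClast and log AUCinf for B versus A. Neither Vz/F nor CL/F enters that model. Both are only summarised descriptively.

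**The case for a change.** The best case for acting is that the formula as printed conflicts with the unit printed beside it, and that correcting it would touch only two table cells. It is the only definition of Vz/F in the documents, and Section 7.1 allows software other than the named package, so someone could code it by hand. Conversion from PDF may have flattened a stacked fraction, but that is a weak defence: the AUCextr% row of the same table kept its brackets, and the other fractions are written inline.

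What stands is that the notation is loose and that the literal reading is wrong. What does not follow is a realistic risk to the results. Anyone able to code noncompartmental parameters knows that volume is clearance divided by λz, and the units column says the same. The named software and the sponsor's guidelines do not depend on this table cell, and a literal slip would produce an implausible number. As for CL/F, the adjacent Vz/F row names AUCinf, and a total clearance after a single dose is naturally based on total exposure. An analyst would fill that gap the same way.

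**Conclusion.** This is a clerical slip and no change to the plan follows. The Vz/F row lacks brackets, and its intended meaning, Dose/(AUCinf × λz), can be recovered from the table itself. The factor of 1517 is arithmetically right at 27 h with time in hours, but it describes a misreading that the stated units rule out. The unspecified AUC in the CL/F row is a small gap, worth about 2.5% at 27 h.

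The 2.5% rests on a mono-exponential tail and on concentrations measurable to 144 h. It would be larger with a longer half-life or an earlier last measurable sample. The judgement that Vz/F will be computed correctly rests on the use of standard noncompartmental software or equivalent practice. The conclusion about the trial's results rests on neither, because the food-effect ratios and their intervals use only Cmax, AUClast and AUCinf.
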